12.4 Planned Analysis

The primary statistical effect of interest is the change in TIR resulting from the transition from AIDANET to AIDANET+BPS_RL and vice versa. Thus, the analysis will involve use of repeated measures General Linear Model (GLM), with emphasis on the interaction corresponding to the crossover design. The analysis will use covariates, e.g., baseline HbA1c, gender, and TIR within the first week on AIDANET alone (see Figure 1).

All secondary outcomes will be similarly analyzed. In particular, the CGM-based metrics of the last 3 days on AIDANET will be compared to the last 3 days on AIDANET+BPS_RL using repeated measures CLM with covariates as described above. If the distribution of an outcome is not suited for GLM (e.g., profound skewness, or atom at boundary), we will perform paired Wilcoxon signed rank test (and lose the capacity to use covariates) to test difference in the median instead of the mean; this is expected for time < 54 mg/dl and possibly time >250 and 300 mg/dL.

We do not plan to correct for multiple comparisons. We do not expect substantial missing values in this supervised study, but if more than 20% of the data for the primary outcome is missing, we will consider switching to mixed models that handle missing data better.

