2.2 Specific Aims and Hypotheses

Aim 1: To evaluate the performance (safety, efficacy) of AIDANET+ BPS_RL used as FCL.

Hypothesis: AIDANET+ BPS_RL use will result in equivalent or better Time in Range (TIR) than AIDANET (including current BPS) during two 18-hour hotel sessions (randomized crossover).

[figure not shown]
Aim 2: To evaluate the safety and efficacy of AIDANET+ BPS_RL at home.

Hypothesis: AIDANET+ BPS_RL use will result in equivalent or better TIR than AIDANET alone, during a week of At-Home use (repeated measures).

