5.1 AIDANET use at home

Visit 3

Participants will use the study equipment with the AIDANET algorithm for 7 days/6 nights. Participants will be instructed to follow their normal routine involving diet, exercise, and insulin administration during this week.

Participants using their personal Dexcom CGM will share their CGM download data with the study team at the completion of this week.

Remote monitoring will be in place during this At-Home Period as detailed in section 7.2. Participants will be advised to call the study team if they have any questions or concerns.

Approximately 24-48 hours after initiating the system, the study team will contact the participant via phone/email/text/video to assess adverse events, adverse device effects, and device issues. If the participant chooses, this visit can occur at the clinical site. The study team will verify the following information:

1. Review system use
2. Inquire about any changes to the participant's medical history
3. Inquire about any changes to the participant's medication
4. Review of CGM data
5. Review of hypoglycemic events
6. Review of hyperglycemic events

Any other relevant contacts during the week will be recorded on the CRF and summarized as appropriate (e.g. contact that is not a scheduling or supplies issue will not be recorded).

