12.3 Outcome Measures

The primary outcome will be the CGM-measured time in range (TIR, 70-180 mg/dL) during the 18-hour hotel sessions on AIDANET or AIDANET+BPS_RL (Figure 1). The time periods begin at 6 PM and end at noon on the next day, thereby covering two meals – dinner and breakfast. These

time periods are expected to reflect well any differences, e.g., potential TIR improvement, that can be attributed to the new BPS_RL.

Secondary outcomes from the 18-hour Hotel Sessions of the study (see Figure 1):

Descriptive glycemic analyses for certain efficacy measures recommended by the International Consensus on TIR, to which we contributed, will be tabulated for each subject based on CGM data, including:

- percentage of readings in other ranges, including time below range (TBR, < 70 mg/dl), time above range (TAR, > 180 mg/dl) and time in tight range 70-140 mg/dl;
- mean glucose; glucose variability measured by coefficient of variation;
- percentage of readings <54 mg/dl (i.e., level 2 hypoglycemia)
- percentage of readings >250 and >300 mg/dl (i.e., level 2 hyperglycemia).

Secondary outcomes from the 1-week Home Sessions of the study (see Figure 1):

All CGM-based glycemic metrics computed during the Hotel sessions of the study will be computed during the Home sessions as well. *The last 3 days of each week at home on AIDANET or AIDANET+BPS_RL will be used for the analyses described below.*

We will also observe, record, and tabulate any system errors that would inform us whether system fixes would be needed prior to deployment in a subsequent larger study. We will tabulate technical performance metrics including:

- Malfunctions requiring study team contact and other reported device issues;
- Percent time in closed-loop and any other relevant operational modes;
- Rate of relevant AIDANET+BPS_RL failure events and alarms per 24 hours;

The technical performance, errors, and glycemic analyses will be also split by time of the day: daytime vs. night-time.

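### The home-week TIR comparison adjusts for first-week AIDANET TIR, a covariate that contains the AIDANET outcome itself

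*Combined protocol and SAP*

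**What the plan says.** Section 12.4 (Planned Analysis) introduces the covariates for the repeated-measures model: "The analysis will use covariates, e.g., baseline HbA1c, gender, and TIR within the first week on AIDANET alone". It then extends the approach to the secondary outcomes. The home metrics from the end of the AIDANET week are compared with those from the "last 3 days on AIDANET+BPS_RL using repeated measures CLM with covariates as described above" (CLM is presumably a misprint for GLM).

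Section 12.3 (Outcome Measures) fixes the home window: "The last 3 days of each week at home on AIDANET or AIDANET+BPS_RL will be used for the analyses described below". Section 5.1 gives the length of the AIDANET week: "Participants will use the study equipment with the AIDANET algorithm for 7 days/6 nights". Section 2.2 states the Aim 2 hypothesis as "equivalent or better TIR than AIDANET alone, during a week of At-Home use (repeated measures").

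No text removes first-week TIR from the home model. Section 12.4 does not say whether covariates are centred or whether they interact with condition. A covariate-free route exists only for outcomes whose distribution does not suit the GLM: "we will perform paired Wilcoxon signed rank test (and lose the capacity to use covariates").

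**The concern.** For home TIR, the first outcome is the mean of the last three days of the AIDANET week, and the covariate is TIR over that whole week. A participant who happened to have a good AIDANET week has a high covariate and, by regression to the mean, a smaller or negative change afterwards. The change is therefore negatively related to the covariate even when the two systems perform identically.

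The home comparison is exposed because every participant has the same order at home, AIDANET and then AIDANET+BPS_RL. There is no sequence contrast to carry the treatment effect. It is the plain within-participant effect, which in a model with covariate-by-condition terms is the intercept of the regression of change on the covariate. At stake are the standard error, and under one coding the estimate itself, for home TIR, which is the subject of Aim 2's hypothesis.

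**Working it through.** **The plan's own figures.** The plan gives none for the home test. Its sizing figures concern the hotel outcome: f = 0.2, N = 50 for the later study, and power below 50% here. They reproduce approximately. Assume two-sided 5%, 80% power and within-participant correlation 0.5. Then d = 0.4, dz = 0.4/√(2 × 0.5) = 0.4, and N = (1.960 + 0.842)²/0.4² ≈ 49 (52 with the t distribution). Pilot power is 0.30 at n = 15 and 0.32 at n = 16. None of this enters the check below.

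**Set-up.** Let W be mean TIR over days 1-7 of the AIDANET week, Y1 the mean of days 5-7 of that week, Y2 the mean of three days in the later week, and D = Y2 − Y1. The windows come from sections 12.3 and 5.1. The following are assumed, because the documents do not state them: mean TIR 70%; between-participant SD s = 3-10, week-to-week SD k = 0-8 and day-to-day SD d = 10-12 percentage points; independent days; no true difference. W is taken as the only covariate.

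**Formulas.**
- Cov(D, W) = −(k² + d²/7)
- Var(W) = s² + k² + d²/7
- Var(D) = 2k² + 2d²/3
- Slope of D on W: b = −(k² + d²/7)/Var(W)
- R² = (k² + d²/7)²/[Var(W) × Var(D)]

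**Coding 1, W as a main effect only.** W is constant within a participant, so it cancels from D and the estimate is the paired mean difference. In one simulated dataset with a true gain of 5 points, both estimates were 4.84. A mixed-model fit of that dataset gave SE 2.19 against 2.29 for the paired analysis, because the participant variance was estimated at essentially zero. The overlap did not move the estimate.

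**Coding 2, W by condition, W mean-centred.** The estimate is still the mean of D, but the model's SE is based on Var(D)(1 − R²), although the mean of D varies with the full Var(D). Type I error is P(|t| > t_crit × √(1 − R²)) on n − 2 df.

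**Coding 3, W by condition, uncentred.** The tested effect is the predicted change at TIR = 0%. Its expected value with no true difference is −70b.

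Worked example for s = 3, k = 8, d = 10, n = 16:
- k² + d²/7 = 64 + 14.29 = 78.29
- Var(W) = 9 + 78.29 = 87.29; Var(D) = 128 + 66.67 = 194.67
- b = −78.29/87.29 = −0.897, so the spurious effect at TIR = 0 is 70 × 0.897 = 62.8 points
- R² = 78.29²/(87.29 × 194.67) = 0.361 and √(1 − 0.361) = 0.80, so the SE is about 20% too small
- 2.145 × 0.80 = 1.715, which gives a two-sided type I error of 10.8% on 14 df

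Results for n = 16. The last column is from simulation, 40,000 trials per setting:

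| s, k, d | R² | Type I, centred | Spurious effect, uncentred | Type I, uncentred |
|---|---|---|---|---|
| 10, 0, 10 | 0.027 | 5.3% | +8.8 | 9.2% |
| 8, 0, 12 | 0.052 | 5.5% | +17.0 | 13.3% |
| 8, 5, 10 | 0.128 | 6.5% | +26.6 | 27.8% |
| 5, 5, 12 | 0.202 | 7.6% | +45.2 | 43.0% |
| 5, 8, 10 | 0.305 | 9.5% | +53.1 | 62.9% |
| 3, 8, 10 | 0.361 | 10.8% | +62.8 | 73.3% |

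The simulation agrees with the formulas for the centred model and the spurious effect. Results at n = 15 are similar: 5.3-10.9% centred, 8.9-70.0% uncentred. In the dataset with a true 5-point gain, the centred model gave 4.84 (SE 2.00) and the uncentred model 57.4 (SE 22.2).

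**Checks on remedies.** The plain paired comparison held 4.9-5.1% in every setting. Restricting the covariate to days 1-4 is not a full cure: with the covariate centred and a shared week effect present, type I error was still 5.4-7.8%. A TIR measured before the study and not overlapping the outcome held about 5%. It must still be centred: left uncentred, power for a true 5-point gain fell from about 40% to 5.7%.

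**The case against.** The strongest reply is that the plan does not commit to a harmful coding. The covariates are given as examples, and neither interaction terms nor centring is specified. If first-week TIR enters only as a main effect, it does nothing to the contrast. If it is centred, the estimate is still the raw paired difference and the error rate rises modestly. The large figures need an interaction, no centring and assumed SDs. A gain of 53 points on a mean of 70% would be visibly impossible. All of this stands, and it rules out the reading that a reader might infer, namely that the Aim 2 test is invalid. That is true of one coding only.

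The scope is also limited. Exact overlap concerns home TIR. Other home metrics share days with the covariate and correlate with it, but it does not contain them. Outcomes sent to the Wilcoxon test use no covariates. Home TIR is a secondary outcome without a stated alpha or margin, and section 12.6 judges TIR by the sign of the difference, whatever the p-value.

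A reader might also infer that the covariates cost the hotel primary analysis precision. The documents do not support this. The first week precedes the hotel sessions and is not part of that outcome. Participant-level main effects do not consume within-participant degrees of freedom in a complete crossover, and a loss would need covariate-by-period terms that the plan does not state.

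What the reply does not supply is a reason to keep the covariate. No coding makes it useful here, and open coding could be settled after the data are seen.

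**Conclusion.** The concern holds for the home TIR comparison. The overlap follows directly from sections 12.3 and 12.4 and needs no assumption beyond reading the first week as the whole week. Its effect ranges from none (main effect only), through type I error of about 5-11% (centred, interacting with condition), to a false gain of about 9-63 points with type I error of about 9-73% (uncentred, interacting). The sizes rest on the assumed mean and SDs; the direction does not, since the covariance between change and covariate is negative under any values in this model. The sign-based success criterion is unaffected unless an uncentred estimate is reported as the difference. This is a moderate correction to a secondary (Aim 2) analysis in a pilot, and it gives no ground for changing the hotel analysis or its covariates.

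**What to change.** In section 12.4, state that first-week AIDANET TIR is not a covariate in the home TIR comparison. Make the reported result the paired difference, last three days on AIDANET+BPS_RL minus last three days on AIDANET, with its 95% CI. State whether any remaining covariate interacts with condition and, if so, that it is mean-centred. If a baseline TIR is wanted, use CGM data from before the study; section 3.8 allows its collection but does not require it. Leave the hotel covariates as they are.

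The cost is two or three sentences of wording, with no change to data collection, devices or participants.

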3.2 Participant Recruitment and Enrollment

We will enroll up to 24 participants who have been diagnosed with T1D for at least one year. This enrollment number accounts for dropouts or screen failures that may occur. The goal is to complete a total of approximately 16 participants.

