12.2 Sample Size

We use pilot trials to introduce new technologies, test system component interoperability, and support regulatory approval of larger subsequent studies. Depending on the traceability of the system to previous established technology or components, the pilots can range from a small 5-person 3-day trial, such as the one we used to enable the pivotal trial of Control-IQ, to a multi-center test of pump configurations. This study is directly traceable to the studies described in IDE #G230052 (Neural Net Artificial Pancreas, NAP) and IDE #G240236 (AIDANET), in terms of algorithm functionality – as noted above, the new element is the replacement of the AIDANET built in bolus priming with a new BPS_RL. Thus, based on our experience, we estimate that the completion of N=15 (and recruitment of up to 20) AID system users, will be feasible in terms of first regulatory approval of the new BPS_RL, and sufficient to assess the effect size of the transitions between the existing AIDANET and the new AIDANET+BPS_RL.

The overall aim is to achieve effect size $f = 0.2$ on the primary outcome described below. If this effect size is confirmed, then a subsequent larger study, which is planned within the scope of the NIH/NIDDK Grant RO1 DK 133148 supporting this pilot, will need a sample size of N=50 completed participants to establish superiority of the new AIDANET+BPS_RL over its current version.

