12.6 Criteria for Success

The success criteria will include no critical system errors and the following performance criteria, which factor in likely inter-day variability for each participant and are consistent with the recommendations of the International Consensus on TIR:

- Positive difference in TIR between AIDANET+BPS_RL and AIDANET, e.g. TIR on AIDANET+BPS_RL greater than TIR on AIDANET, regardless of p-value;
- Difference in TBR between AIDANET+BPS_RL and AIDANET < 3 percentage points;
- Positive difference in TAR between AIDANET+BPS_RL and AIDANET.

Formal power analysis is not applicable to this pilot study – with this sample size a statistically significant result is not expected (Power less than 50%). The point of the study is to show feasibility of the new BPS and assess whether effect size $f=0.2$ is achievable in a subsequent study.

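### For time <54 mg/dL, section 12.4's difference in the median is fixed at zero whenever most participants have none in both sessions, and the signed-rank test does not test it

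*Combined protocol and SAP*

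**What the plan says.** Section 12.3 lists "percentage of readings <54 mg/dl (i.e., level 2 hypoglycemia") among the secondary outcomes. It is computed for the 18-hour hotel sessions and for the last 3 days of each home week. The section also says that such measures "will be tabulated for each subject based on CGM data".

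Section 12.4 plans a repeated-measures GLM with covariates for the secondary outcomes, with a fallback: "If the distribution of an outcome is not suited for GLM (e.g., profound skewness, or atom at boundary"), a paired Wilcoxon signed-rank test is used instead. Its purpose is given as "to test difference in the median instead of the mean; this is expected for time < 54 mg/dl", and possibly also for time above 250 and 300 mg/dL. No other between-algorithm effect measure is named for outcomes that take this route.

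Section 12.6 sets a hypoglycaemia success criterion for time below 70 mg/dL only (a difference under 3 percentage points). It also says that a significant result is not expected, with power below 50%.

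The number of completers is given in two ways. Section 12.2 plans "completion of N=15 (and recruitment of up to 20) AID system users"; section 3.2 says "The goal is to complete a total of approximately 16 participants". The conclusion is the same for 15 and 16.

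**The concern.** Section 12.4 foresees a cluster of zeros for level 2 hypoglycaemia, then names an effect measure that such a cluster can hold at zero. A median says nothing about a minority. If the new priming bolus adds time below 54 mg/dL in a few participants and most have none, the median does not move.

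The test and its description also do not match. The signed-rank test drops tied pairs, ranks the remaining absolute differences and obtains its null distribution by flipping signs. That null is symmetry of the paired differences about zero.

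At stake is how informative the comparison is. In a pilot where p-values are expected to say little, the effect estimate carries the evidence, and a median difference of 0 beside a large p-value could be taken as reassurance when the follow-on study is planned.

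**Working it through.** **The plan's own figure.** The documents give no figure for time below 54 mg/dL. The nearest is power below 50% for effect size f = 0.2 on TIR. For a two-period repeated-measures F test the noncentrality is f² × N × 2/(1−ρ). With ρ = 0.5 (assumed) and two-sided alpha 0.05 (assumed; Chapter 12 states none):
- N = 15: 0.04 × 15 × 2/0.5 = 2.40, power 30%.
- N = 16: 0.04 × 16 × 2/0.5 = 2.56, power 32%.

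For ρ from 0 to 0.7 power is 17% to 49%, so the statement reproduces. At ρ = 0.8 it would be 62% to 66%.

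**When the median is fixed.** With N = 16 the median averages the 8th and 9th ordered values. If at least 9 participants have zero in both sessions, those two values are zero in each session. They are also zero among the paired differences, whatever the signs of the other 7. With N = 15, 8 such participants suffice.

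**Fixed examples, N = 16.** Affected participants have values evenly spaced from 0.5% to 1.6% on AIDANET (assumed), all tripled on AIDANET+BPS_RL.

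| Affected | Both median measures | Mean, AIDANET | Mean, AIDANET+BPS_RL | Mean paired difference | Exact signed-rank p |
|---|---|---|---|---|---|
| 4 | 0 | 4.20/16 = 0.26% | 12.60/16 = 0.79% | 8.40/16 = +0.53 points | 0.125 |
| 7 | 0 | 7.35/16 = 0.46% | 22.05/16 = 1.38% | 14.70/16 = +0.92 points | 0.016 |

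With 4 affected, the Hodges-Lehmann estimate over all pairs is 0 as well; with 7 it is +0.87 points.

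**Smallest attainable p.** With m untied pairs the minimum two-sided exact p is 2/2^m: 0.0625 for m = 5 and 0.031 for m = 6. If each participant has an untied pair with probability q, significance is out of reach with probability P(X ≤ 5), X ~ Binomial(N, q):
- q = 0.2: 0.92 for N = 16, 0.94 for N = 15.
- q = 0.3: 0.66 for N = 16, 0.72 for N = 15.

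**Simulation, N = 16.** Assumptions: latent within-person correlation 0.3; time below 54 mg/dL, when present, exponential with mean 2 percentage points.

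| Share with any time <54, AIDANET vs AIDANET+BPS_RL | Median paired difference exactly 0 | Signed-rank p<0.05 |
|---|---|---|
| 10% vs 20% | 99.6% of trials | 3% |
| 10% vs 30% | 95% | 14% |
| 20% vs 40% | 85% | 15% |
| 10% vs 45% | 67% | 42% |

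In the last row both population medians are 0, so equality of medians is true, yet the test rejects in 42% of trials. It is therefore not a test of medians.

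**How far this reaches.** A second simulation (N = 16, latent correlation 0.5) tripled the outcome in two ways and recorded how often the difference in medians was exactly 0.
- Tripling the time in the same share of participants: 100% of trials at a starting share of 10%, 99% at 20%, 87% at 30%, 56% at 40%, 23% at 50%.
- Tripling the share affected: 92% at 10%, 56% at 15%, 14% at 20%, 0.3% at 30%.

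**An interval for the mean.** Under the assumptions of the first simulation, a percentile-bootstrap one-sided 95% upper bound for the mean paired difference covered the true value in only about 81% to 88% of trials.

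**The case against.** The strongest case on the other side has four parts.

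1. *The zero median depends on an unstated rate.* An atom at the boundary need not be a majority, and the documents give no expected share. The home comparison uses 3 days, or 72/18 = 4 times the hotel window, so zeros should be fewer there. This stands. A reader might infer that the plan would show no difference even if level 2 hypoglycaemia tripled. The documents do not support that in general: it needs a majority still at zero after the increase, and it fails once the affected share triples from above about one in six.

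2. *The test is not blind.* Six of 16 participants rising with 10 tied gives p = 0.031 while both medians are 0. This also stands. A reader might infer that the test cannot see harm confined to a minority. It can; what it lacks is power when few pairs are untied, and section 12.6 already says that significance is not expected.

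3. *The data stay visible.* Section 12.3 plans per-subject tabulation, and with about 16 participants that shows who had any time below 54 mg/dL. This limits the harm. A listing is still not a between-algorithm summary, and section 12.4 names only the median.

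4. *No decision rests on this p-value.* The criterion in section 12.6 uses time below 70 mg/dL, which includes every reading below 54, and needs no p-value. Nothing in the plan says that a non-significant result will be read as safety. This stands as to severity. The criterion would still admit the 0.92-point rise in the example above if time between 54 and 70 mg/dL were unchanged, so it does not replace a usable summary of level 2 hypoglycaemia.

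**Conclusion.** The point holds, conditionally, and is minor. If most participants have no time below 54 mg/dL in both sessions, the effect named in section 12.4 is 0 by construction. The signed-rank test addresses symmetry of paired differences and cannot reach two-sided 0.05 with five or fewer untied pairs. At N = 16 that situation has probability 0.92 if 20% of pairs are untied and 0.66 if 30% are.

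The affected shares, amounts, within-person correlations and the two-sided 0.05 level are assumptions. The minimum p-values and the order-statistic argument are not. The plan contains no commitment to treat a null result as evidence of safety, so the defect lies in the wording and the summary measure, not in a safety decision.

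**What to change.** In section 12.4, for outcomes with an atom at zero (time below 54 mg/dL, and above 250 or 300 mg/dL where this occurs), replace the difference in the median as the effect measure with:

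- the number of participants with any such time on each algorithm, and the numbers with more and with less of it on AIDANET+BPS_RL;
- the mean paired difference in percentage points.

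Label any interval for the mean as approximate, given the bootstrap coverage shown above. If the signed-rank p-value is kept, describe it as a test of symmetry of the paired differences and state that non-significance is not evidence of no excess.

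The cost is a sentence or two in section 12.4 and a few table rows from CGM data already collected. The downside is that one extreme participant can drive the mean; the counts beside it would show this.
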